5.1.1 Pembrolizumab

Pembrolizumab will be administered as a 30-minute IV infusion. Every effort will be made to target infusion timing to be as close to 30 minutes as possible. However, given the variability of infusion pumps, a window of -5 minutes and +10 minutes is permitted (i.e. infusion time is 30 minutes: -5 min/+10 min). All IV infusion treatments will be administered on an outpatient basis.

Phase 2, Pembrolizumab, Vactosertib

Note: Treatment with pembrolizumab may be administered up to 3 days before or after the scheduled Day 1 of each cycle due to administrative reasons (such as holidays).

5.1.2 Vactosertib

Vactosertib will be administered once daily at 200 mg PO for 5 days followed by a 2-day resting period (5 days on/2 days off) for two weeks during the neoadjuvant treatment phase.

During the optional adjuvant treatment phase, vactosertib will be administered once daily at 200 mg PO (dose level -1) for 5 days followed by a 2-day resting period during Cycle 1. If no significant drug-related toxicities are observed, vactosertib will be administered twice daily at 200 mg PO (dose level 0) for 5 days followed by a 2-day resting period (5 days on/2 days off) for up to 8 cycles.

Please see Section 5.2, Dose Modifications and Dosing Delays for additional details.

5.1.3 Other Modality(ies) or Procedures

Patients are expected to undergo standard of care surgical resection of liver metastases within 4-6 weeks of the final chemotherapy administration (if applicable) and approximately 2 weeks (minimum 1 week) after their neoadjuvant dose of pembrolizumab-base treatment. Standard of care operative plan is at the discretion of the treating surgeon.

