Study Drugs	
Neoadjuvant pembrolizumab will be administered at a fixed dose of 200 mg (IV) for 1 cycle plus 200 mg vactosertib (PO QD, 5 days per week x 2 weeks).
 
Adjuvant pembrolizumab (400 mg IV) + vactosertib (200 mg PO QD Cycle 1, 5 days per week, Cycles 2 and beyond 200 mg BID, 5 days per week) will be administered for up to eight 6-week cycles.

Phase 2, Pembrolizumab, Vactosertib

Safety Assessments	Safety assessments will include adverse events, clinical laboratory evaluations, and vital signs.
Efficacy Assessments	Objective response rate, pathologic response rate, R0 resection rate, and 1-year and 2-year RFS.
Unique Aspects of this Study	This is the first study to evaluate the safety and efficacy of pembrolizumab plus vactosertib following FOLFOX chemotherapy in patients with metastatic CRC undergoing liver resection with curative intent. Biopsy of a liver metastasis prior to administering pembrolizumab plus vactosertib and resection of the liver metastases following 1 cycle of pembrolizumab plus vactosertib will enable extensive scientific correlatives.

Study Schema

The above timeline is approximate with further guidelines below:

- A screening computed tomography (CT) chest/abdomen/pelvis with intravenous (IV) contrast must be performed and reviewed to confirm candidacy for hepatic resection prior to study entry.
- If chemotherapy is a direct lead-in to study enrollment, then liver resection surgery should be performed within 4-6 weeks of the final chemotherapy administration. During this 4-6 week window, 1 cycle of pembrolizumab plus vactosertib will be administered approximately 2 weeks (minimum 1 week) after the last dose of chemotherapy, and surgery will occur approximately 2 weeks (minimum 1 week) after C1D1.
- Labs, including liver function testing will be performed after C1D1, as close to surgery as possible.

Phase 2, Pembrolizumab, Vactosertib

- In the event that the surgery is canceled, and the first liver biopsy yielded adequate tumor material, a second liver biopsy will be requested (same lesion as the first biopsy preferred).
- Participants will be followed for up to 2 years after surgery or will be offered optional adjuvant treatment (described below).

Optional Adjuvant Treatment

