3.4 Duration of Therapy

All participants will receive a single dose of pembrolizumab and 20 doses of vactosertib (QD, 5 days per week for 2 weeks) prior to surgery.

Participants who undergo surgical resection and have adequately recovered from toxicity or complications of a surgery or other procedure, per the assessment of the treating investigator, may receive optional adjuvant treatment of pembrolizumab + vactosertib for up to eight 6-week cycles.

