5.1 Dosage and Administration

Trial treatment should be administered at the time points specified in the Trial Flow Charts (section 6.2). The treatment to be used in this trial is outlined in Table 4 and Table 5. On Day 1 of each cycle, administer vactosertib after the subject completes their pembrolizumab infusion. Vactosertib may be administered as soon as the pembrolizumab infusion is completed. Vactosertib and pembrolizumab may be administered without regard to meals.

Table 4 Main Trial Treatment

Drug	Dose/ Potency	Dose Frequency	Route of Administration	Regimen/ Treatment Period	Use
Pembrolizumab	200 mg	Once	IV infusion	C1D1	Experimental
Vactosertib	200 mg	QD, 5 days per week	PO	C1D1 through C1D14	Experimental

Abbreviation: IV = intravenous, PO = per os, C = cycle, D = day, QD = once a day

Table 5 Optional Adjuvant Treatment Cohort

Drug	Dose/ Potency	Dose Frequency	Route of Administration	Regimen/ Treatment Period	Use
Pembrolizumab	400 mg	Q6W	IV infusion	Up to 8 cycles	Experimental
Vactosertib	200 mg	Cycle 1: QD, 5 days per week Cycles 2+: BID, 5 days per week	PO	Up to 8 cycles	Experimental

Abbreviation: IV = intravenous, PO = per os, C = cycle, D = day, Q6W = every 6 weeks, QD = once a day, BID = twice a day

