6.1.1 Screening Assessments

The screening procedures and assessments must be completed within 28 days prior to the dose of pembrolizumab, unless specified otherwise. Note that the cycle of pembrolizumab-based treatment should begin ≥ 7 days after the final chemotherapy administration.

Note: A screening CT chest/abdomen/pelvis with IV contrast must be performed and reviewed to re-confirm candidacy for hepatic resection prior to liver tumor biopsy.

Screening procedures and assessments:

- Review of eligibility
- Complete physical examination
- Vital sign measurements and weight
- Complete medical history (including MMR/MSI status) and demographics
- Documentation of disease status assessment/measurable disease
- ECOG performance status performed within 7 days prior to treatment administration
- History of prior treatments and any residual toxicity relating to prior treatment. Include number of cycles of FOLFOX/CapeOx received prior to pembrolizumab; interval between last FOLFOX/CapeOx treatment and pembrolizumab; addition of monoclonal antibodies to chemotherapy; growth factor support.
- Baseline medications taken within 28 days of Day 1
- Tumor marker assessments (CEA): also record CEA at diagnosis, prior to and after lead-in FOLFOX/CapeOx (if applicable).
- Complete blood count (CBC) with differential and platelet count
- Hematology labs (other than CBC w/ Diff)
- Blood chemistry assessment, including:
 - Alkaline phosphatase (ALP), aspartate aminotransferase/alanine aminotransferase (ALT/AST), total bilirubin, direct bilirubin (*If total bilirubin is elevated above the upper limit of normal*), calcium, phosphorus, blood urea nitrogen (BUN), creatinine, total protein, albumin, fasting glucose, potassium,

sodium, magnesium, chloride, bicarbonate, uric acid, lactate dehydrogenase (LDH)

- Thyroid function tests: thyroid-stimulating hormone (TSH), free thyroxine (FT4); free and total triiodothyronine (T3)
- Coagulation assessment (prothrombin time [PT], partial thromboplastin time [PTT], international normalized ratio [33])
- Serum Hepatitis assessment, including Hepatitis B surface antigen (HBsAg), Hepatitis B surface antibody (HBsAb), Hepatitis B core antibody (HBcAb), HCV RNA
- Urinalysis
- Serum or urine pregnancy test within 72 hours prior to the start of study drug
- Echocardiogram (ECHO)
- Imaging (CT chest/abdomen/pelvis with IV contrast) for tumor/lesion assessment and to confirm candidacy for liver resection surgery.

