6.2 Trial Flow Chart

Table 10 Main Trial Flow Chart

Trial Period: Treatment Cycle/Visit:	Screening	Preoperative Treatment	Pre-Surgery	Surgery	Post-Surgery Safety F/U	Follow Up Phase ^{a,m}
		C1D1				
Scheduling Window:	-28d to -1d	≥7d post-last chemotherapy	+7-14d post-C1D1	+7-14d post-C1D1, 28-42d post-last chemo	14d ±7d post-op	Q90D ±14d post-op for up to 2y
Directed Medical History	X					
Main Trial Study Informed Consent	X ^b					
Future Biomedical Research consent (optional)	X ^b					
Inclusion/Exclusion Criteria	X					
Demographics and Full Medical History, including MMR/MSI status	X				X ^c	
Prior and Concomitant Medication Review	X ^d	X	X	X	X	X ^k
History of Prior Treatments and residual toxicity to prior treatment	X					
Trial Treatment Administration ^j		X				
Dispense vactosertib supply		X				

Trial Period: Treatment Cycle/Visit:	Screening	Preoperative Treatment	Pre-Surgery	Surgery	Post-Surgery Safety F/U	Follow Up Phase ^{a,m}
		C1D1				
Scheduling Window:	-28d to -1d	≥7d post-last chemotherapy	+7-14d post-C1D1	+7-14d post-C1D1, 28-42d post-last chemo	14d ±7d post-op	Q90D ±14d post-op for up to 2y
Post-study anticancer therapy status						X ^k
Survival Status						X
Review Adverse Events		X	X		X	X ^k
Complete Physical Examination	X					
Directed Physical Examination		X	X		X	
Vital Signs and Weight	X	X	X		X	
ECOG Performance Status	X ⁱ	X	X		X	
Pregnancy Test – Urine or Serum	X					
PT/INR and aPTT	X ⁿ		X			
Hematology, CBC with Differential and platelet count	X ⁿ	X	X		X	X ^a
Comprehensive Serum Chemistry Panel (see Table 12)	X ⁿ	X	X		X	X ^a
Urinalysis	X	X	X		X	X ^a

Trial Period: Treatment Cycle/Visit:	Screening	Preoperative Treatment	Pre-Surgery	Surgery	Post-Surgery Safety F/U	Follow Up Phase ^{a,m}
		C1D1				
Scheduling Window:	-28d to -1d	≥7d post-last chemotherapy	+7-14d post-C1D1, 28-42d post-last chemo	+7-14d post-C1D1, 28-42d post-last chemo	14d ±7d post-op	Q90D ±14d post-op for up to 2y
T3 (free and total), FT4 and TSH	X	X	X		X	X ^a
Tumor Marker: CEA p.	X	X	X		X	
Hep B surf Ag, Hep B sur Ab, Hep B core Ab, Hep C RNA	X					
Echocardiogram (ECHO)	X					
Electrocardiogram (ECG)		X ⁱ				
Disease Status Assessment/ Measurable disease	X		X			X
Tumor Imaging ^h	X ^g					X
Archival Tissue Collection		X ^o				
Biopsy of Liver Metastasis	X				X ^e	
Hepatic metastasectomy				X		
Correlative Studies: Blood Collection		X	X		X	X ^k
Correlative Studies: Stool	X		X		(X)	

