Trial Period: Treatment Cycle/Visit:	Screening	Preoperative Treatment	Pre-Surgery	Surgery	Post-Surgery Safety F/U	Follow Up Phase ^{a,m}
		C1D1				
Scheduling Window:	-28d to -1d	≥7d post-last chemotherapy	+7-14d post-C1D1	+7-14d post-C1D1, 28-42d post-last chemo	14d ±7d post-op	Q90D ±14d post-op for up to 2y
Collection and Questionnaire ^f						
Dietary and physical activity questionnaire	X					
Optional Adjuvant TX Recruitment ^{l,m}					X	

Abbreviations: aPTT – activated partial thromboplastin time; CBC = complete blood count; CEA = carcinoembryonic antigen; ECOG = Eastern Cooperative Oncology Group; FT4 = free thyroxine; GI = gastrointestinal; INR = international normalized ratio; LDH = lactate dehydrogenase; MMR = mismatch repair; MSI = microsatellite instability; post-op = post-operation; PT = prothrombin time; T3 = triiodothyronine; TSH = thyroid stimulating hormone; DC = discontinuation; F/U = follow-up; TX = treatment; d = day(s); w = week(s); y = year(s); c = cycle.

- Follow-up: every effort should be made to collect information regarding disease status for 1 year after pembrolizumab dosing, progressive disease or death, whichever comes first. Follow-up assessments and subsequent anti-neoplastic therapy are at the discretion of the treating investigator. It is advised that patients should be assessed every 90 days (±14 days) for 1 year after liver resection surgery by radiologic CT imaging with IV contrast to monitor disease status. Additional post-operative chemotherapy will be at the discretion of the treating physician. Information regarding post-study anti-neoplastic treatment will be collected if such treatment is initiated. Safety labs and correlative labs will be collected up to 1 year post-pembrolizumab.
- Screening procedures and assessments must be completed within 28 days prior to C1D1. C1D1 should occur approximately 2 weeks (minimum 1 week) after the final chemotherapy administration (if applicable). Screening CT chest/abdomen/pelvis with IV contrast must be performed and reviewed to confirm candidacy for hepatic resection prior to liver tumor biopsy. Every effort shall be made to collect future biomedical research samples, but failure to collect this sample due to patient refusal or logistical constraints shall not constitute a protocol deviation or violation and does not prevent the patient from enrolling on-study.

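### Surgery is permitted from 7 days after C1D1, when only 5 of 10 scheduled vactosertib doses have been given, and in lead-in patients Table 10 leaves no valid surgery date if C1D1 is 7-13 days after chemotherapy

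*Combined protocol and SAP*

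**What the plan says.** **Vactosertib before surgery.** Table 4 in Section 5.1 sets the neoadjuvant period as "C1D1 through C1D14". Section 5.1.2 gives one dose a day, 5 days on and 2 off, for two weeks. Section 3.4 states: "All participants will receive a single dose of pembrolizumab and 20 doses of vactosertib", all before surgery, and repeats the once-daily, 5-day, 2-week schedule beside that count.

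**Surgery after C1D1.** The Study Schema says "surgery will occur approximately 2 weeks (minimum 1 week) after C1D1". Section 5.1.3 places surgery "approximately 2 weeks (minimum 1 week) after their neoadjuvant dose of pembrolizumab-base treatment", Section 6.1.4 agrees, and neither gives a maximum. Table 10 (Section 6.2) does: its surgery column reads "7-14d post-C1D1, 28-42d post-last chemo".

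**C1D1 after chemotherapy.** Section 6.1.1 says the cycle "should begin ≥ 7 days after the final chemotherapy administration". Table 10 gives "≥7d post-last chemotherapy" with no upper limit. The Schema, Section 6.1.2 and a footnote to Table 10 set a target of about 2 weeks. Lead-in chemotherapy is not required (Section 3.3.1, criterion 2a), and the text applies the chemotherapy windows only where applicable.

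**Incomplete courses.** Section 6.1.4 lets surgery proceed if vactosertib is held for toxicity. Section 8.4.1 defines the primary set as all patients with evaluable paired specimens and sets no exposure condition.

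**The concern.** The primary objective is the TIL change induced by the combination, measured in tissue taken at surgery. If surgery can come before the last scheduled vactosertib dose, the post-treatment specimens are a mixture: all follow the single pembrolizumab dose, but some follow only part of the vactosertib course. Section 3.4 says this does not happen, while Table 10 permits it. With 17 evaluable patients, a few such specimens could leave a negative result open to two explanations, no effect or too little exposure, and the plan has no listing or analysis to tell them apart.

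Table 10 also sets three intervals that must hold together in a patient with lead-in chemotherapy. For some C1D1 dates that it allows they cannot, so a site would have to deviate.

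**Working it through.** **Step 1: dose count.** Inputs: one dose a day, 5 days a week, 2 weeks (Sections 3.4 and 5.1.2).

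1 × 5 × 2 = 10 doses. Section 3.4's figure of 20 is not reproduced. Starting on Day 1, the doses fall on Days 1-5 and 8-12.

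**Step 2: doses taken before surgery.** With a gap of g days after C1D1, surgery is on cycle day 1 + g. Doses on earlier days are counted.

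| Gap g | Surgery on | Doses before surgery |
|---|---|---|
| +7 | C1D8 | 5 of 10 |
| +8 | C1D9 | 6 of 10 |
| +9 | C1D10 | 7 of 10 |
| +10 | C1D11 | 8 of 10 |
| +11 | C1D12 | 9 of 10 |
| +12 to +14 | C1D13 to C1D15 | 10 of 10 |

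Five of the eight permitted gaps come before the scheduled course is complete.

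**Step 3: joint feasibility of the Table 10 windows, lead-in patients.** Let c be the days from last chemotherapy to C1D1. Table 10 requires c ≥ 7, 7 ≤ g ≤ 14 and 28 ≤ c + g ≤ 42.

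- c = 7: latest surgery is 7 + 14 = day 21. c = 13: 13 + 14 = day 27. Both are before day 28, so c = 7-13 has no valid date.
- c = 14 (the stated target): only g = 14 fits, since 14 + 14 = 28. This is a full course.
- c = 15 and c = 16: g is at least 13 and 12, again a full course.
- c = 17: g = 11-14, the first C1D1 date at which a partial course fits the windows.
- c = 21-28: every gap from 7 to 14 fits.
- c = 31: g is at most 42 − 31 = 11. c = 35: g is at most 7. So c = 31-35 forces surgery before the last scheduled dose.
- c > 35: the earliest surgery is day 36 + 7 = 43 or later, so there is no valid date.

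The windows can therefore be met for c = 14-35, and met with all 10 doses (g ≥ 12) for c = 14-30. If Section 6.1's general ±3 days is assumed to widen the gap after C1D1 to 4-17 days, with 28-42 kept, the feasible range becomes c = 11-38. Days 7-10 still fail.

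**Step 4: where early resection can occur.** In lead-in patients, surgery at +7 meets the windows only for c = 21-35. Without lead-in chemotherapy only the C1D1 interval applies, so +7 is always permitted.

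**Step 5: illustrative power.** Section 8.2.1 has n = 17, 10% against 40%, a one-sided binomial test at 0.05 and stated power 0.91. The exact test rejects at 5 or more responders (type I error 0.022; at 4 or more it is 0.083) and has power 0.874. A one-sided arcsine approximation gives 0.911, so the stated figure appears to be approximate.

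Assumptions, none taken from the documents: full-course patients respond at 40%, and k of the 17 have a partial course and respond at 20-30%. Power = P(X + Y ≥ 5), with X ~ Bin(17 − k, 0.4) and Y ~ Bin(k, p).

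| k | p = 0.2 | p = 0.3 |
|---|---|---|
| 0 | 0.874 | 0.874 |
| 3 | 0.81 | 0.84 |
| 6 | 0.71 | 0.80 |

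**The case against.** A reader might infer that the Table 10 windows can never all be met. The documents do not support that. Every C1D1 date from day 14 to day 35 has at least one valid surgery date, and this range includes the 2-week target. The 14-day cap stands only in Table 10. The text gives an approximate interval with a minimum, and the Schema calls its timeline approximate. Under the text, C1D1 on day 7 and surgery on day 28 would miss only the approximate 2-week target. This stands, and it makes the window conflict a narrow one between table dates.

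In lead-in patients the two problems also largely exclude each other: C1D1 on days 14-16 forces a full course. This stands too. Early resection mainly concerns patients without lead-in chemotherapy or with C1D1 later than the target.

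A partial course affects vactosertib only, since pembrolizumab is given on C1D1, and two weeks is the plan while one week is the floor. Including every evaluable pair whatever the exposure is a defensible treatment-policy choice, and Section 6.1.4 accepts courses cut short by toxicity. But the plan never states that choice, and courses cut short by scheduling are not addressed.

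A reader might also infer that early resection dilutes the response rate and costs a known amount of power. The documents give no relation between days of vactosertib and TIL response, no expected number of early resections and no response rate for them. The power table also uses the binomial test of Section 8.2.1, whereas Section 8.4.2 describes a paired t-test and a signed-rank test, so it does not describe the analysis written there.

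**Conclusion.** The point holds as a contradiction between scheduling rules and a gap in the analysis plan. By day count alone, permitted surgery dates allow vactosertib exposure from 5 to 10 of 10 scheduled doses, against Section 3.4's statement that all participants receive the course first. Section 3.4's 20 doses also contradicts the schedule printed beside it. For lead-in patients, Table 10 admits C1D1 dates (days 7-13 and after day 35) with no valid surgery date, and others (days 31-35) where the only valid dates come before the last scheduled dose.

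These counts assume dosing starts on Day 1 and follows the 5-on, 2-off pattern. The effect on the primary result is unknown. Under the assumed 40% and 20-30% response rates, exact power would fall from 0.874 to 0.81-0.84 with 3 partial courses and to 0.71-0.80 with 6. That shows sensitivity and is not a forecast.

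**What to change.** 1. Reconcile the Study Schema, Sections 3.4, 5.1 (Table 4), 5.1.2, 5.1.3, 6.1.1 and 6.1.4, and Table 10, so that the dose count, the vactosertib period, the surgery interval and the chemotherapy intervals agree. Which of them moves is for the sponsor.
2. In Section 8.4.1, state whether specimens taken before the scheduled course ends count in the primary set, whatever the reason the course was unfinished.
3. Record for each patient the vactosertib doses taken and the days from C1D1 to tissue collection, and list both with the primary result.
4. Add an analysis in patients who finished the scheduled course before tissue collection. Label it supportive, because it selects on post-baseline events and has fewer patients.

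**Cost.** Wording changes, one listing and one supportive analysis, with no change to sample size. Dates should already be available. Table 10 shows vactosertib being dispensed but no diary or pill count, so recording doses taken may need a new case report form field.

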5.1.4 Dose Limiting Toxicity

As the toxicities of pembrolizumab are well-established and not necessarily dose-dependent, this study will not use formal dose-limiting toxicity definitions according to NCI CTCAE grading criteria. However, to avoid compromising patient safety in this potentially curative setting, early stopping rules will be followed such that the study will be stopped, and this approach re-evaluated, if 2 or more of the first 6 patients experience any 1 of the following:

- A delay in planned surgery beyond the 8-week window after final chemotherapy treatment due to any grade toxicity attributable to study treatment. Delays in surgery due to other reasons (scheduling, available operating room time, patient preference) will not count.
- Grade IV and V surgical complications according to Clavien-Dindo classification (Appendix 4).

Note: Surgical complications associated with liver metastasectomy are very common, and we recognize that it may be difficult to attribute any such complications to preoperative administration of pembrolizumab-based treatment. Therefore, the occurrence of such events may not necessarily require stopping the study early, but will be discussed amongst members of the JSC, and Merck with particular attention paid to specific complications such as liver failure, severe colitis, etc.

Moreover, enrollment will be paused for 4 weeks after the sixth patient undergoes surgery (or receives their dose of pembrolizumab-based treatment if unable to undergo surgery). During this interval the study investigators will meet with the participating surgeons and Merck to review the first 6 cases. A recommendation will be made regarding whether or not to enroll additional patients and if any changes are needed to optimize safety or feasibility.

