As in the Nordlinger study, we typically give 6 cycles of FOLFOX to patients with synchronous metastases who are candidates for liver resection [6]. Practice patterns vary greatly for patients with metachronous metastatic disease, based on the specific circumstances, hence flexibly was built into this protocol for feasibility. When applicable, it is then standard to wait 4 to 8 weeks from the time of last FOLFOX administration until surgery. This waiting period represents a window of opportunity to intervene.

Additionally, only about 30% of patients with hepatic metastases treated with curative intent actually achieve cure [2, 27]. Most recurrences occur within 2 years of surgery, so 2-year relapse-free survival (RFS) is a common intervention endpoint [28, 29]. Importantly, despite the high recurrence rate, observation is recommended after surgery for resectable metastases in patients who have received prior oxaliplatin-based therapy because no standard chemotherapy has been proven to improve RFS [30]. Introduction of experimental adjuvant therapy after metastasectomy offers another opportunity for intervention, with a goal to clear any remaining micrometastatic disease.

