8.3 Interim Analyses and Stopping Rules

The trial will be stopped early if 2 of the first 6 patients fail to undergo liver resection surgery within 6 weeks of their final chemotherapy treatment (if applicable) due to AEs attributed to pembrolizumab-based treatment, or experience Grade IV-V surgical complications according to Clavien-Dindo classification attributed to pembrolizumab -base treatment (Appendix 4).

Of particular significance to this study, enrolling patients being treated with curative intent, are perioperative complications attributed to pembrolizumab-based treatment. These may include delaying surgery due to pre-operative AEs and complications during or after surgery attributed to pembrolizumab-based treatment. Early stopping rules have been defined to mitigate risk of perioperative complications. The study will be stopped and the approach will be re-evaluated if 2 or more of the first 6 patients experience any one of the following:

- A delay in planned surgery beyond the 6-week window from final chemotherapy (if applicable), due to any grade toxicity attributable to study treatment. Delays in surgery due to other reasons (scheduling, available O.R time, patient preference) will not count.
- Grade IV and V surgical complications according to Clavien-Dindo classification (Appendix 4). *Note:* Surgical complications associated with liver metastectomy are very common, and we recognize that it may be difficult to attribute any such complications to preoperative administration of pembrolizumab. Therefore, the occurrence of such events may not necessarily require stopping the study early, but will be discussed amongst members of the JSC, with particular attention paid to specific complications such as liver failure, severe colitis, etc.

Enrollment will be paused for 4 weeks after the sixth patient undergoes surgery (or receives their last dose of pembrolizumab if unable to undergo surgery). During this interval the study investigators will meet with the participating surgeons to review the first 6 cases. A recommendation will be made regarding whether or not to enroll additional patients and if any changes are needed to optimize safety or feasibility.

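### The early stopping rule allows toxicity-related surgical delay up to 8 weeks after chemotherapy in section 5.1.4 but only 6 weeks in section 8.3

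*Combined protocol and SAP*

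**What the plan says.** Section 5.1.4 (Dose Limiting Toxicity) stops the study for re-evaluation if 2 or more of the first 6 patients meet either of two criteria. The first is "A delay in planned surgery beyond the 8-week window after final chemotherapy treatment due to any grade toxicity attributable to study treatment". The second is a Clavien-Dindo Grade IV or V surgical complication.

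Section 8.3 (Interim Analyses and Stopping Rules) repeats the rule with the same count and the same consequence, but its delay criterion is "A delay in planned surgery beyond the 6-week window from final chemotherapy (if applicable), due to any grade toxicity attributable to study treatment". Its opening sentence also uses 6 weeks, for patients who "fail to undergo liver resection surgery within 6 weeks of their final chemotherapy treatment (if applicable) due to AEs attributed to pembrolizumab-based treatment".

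Both sections exclude delays caused by scheduling, operating-room time or patient preference. Both pause enrollment for 4 weeks after the sixth patient's surgery so that the first 6 cases can be reviewed.

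Two other places bear on the intended number. The study schema says that, where chemotherapy leads directly into the study, "then liver resection surgery should be performed within 4-6 weeks of the final chemotherapy administration". The rationale in section 1.3 says "it is then standard to wait 4 to 8 weeks from the time of last FOLFOX administration until surgery".

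**The concern.** One stopping rule should have one threshold. Here the treatment section and the statistical section give the same rule with limits two weeks apart, and nothing in either section says which prevails. The patients are being treated with curative intent, and the rule is there to detect early whether the neoadjuvant cycle is pushing surgery back. If the events fall between the two limits, the people deciding would have to choose a threshold after seeing the cases, which a pre-stated rule is meant to prevent.

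A second, smaller difficulty is the starting point of the clock. Both limits count from final chemotherapy, yet inclusion criterion 2a admits patients whose FOLFOX or CapeOx did not lead directly into the study.

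**Working it through.** The plan gives no operating characteristics for the 2-of-6 rule, so there is no stated figure to reproduce. The check is a comparison of texts with simple day arithmetic.

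**Step 1. The two limits in days after final chemotherapy.**
- Section 5.1.4: 8 × 7 = 56 days.
- Section 8.3: 6 × 7 = 42 days.
- Difference: 56 − 42 = 14 days. Toxicity-delayed surgery on days 43 to 56 counts under 8.3 only.

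**Step 2. Which number the rest of the protocol supports.**

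| Place | Timing relative to final chemotherapy |
|---|---|
| Study schema | 4-6 weeks |
| 3.2, accrual suspension | 4-6 weeks (if applicable) |
| 5.1.3, surgery | 4-6 weeks (if applicable) |
| 6.1.4, surgery | 4-6 weeks (if applicable) |
| Table 10, surgery column | 28-42 days |
| 8.4.3, feasibility criterion | 6 weeks (if applicable) |
| 8.3, opening sentence and bullet | 6 weeks (if applicable) |
| 1.3, background on usual practice | 4-8 weeks |
| 5.1.4, stopping rule | 8 weeks |

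Every operative statement outside 5.1.4 uses 6 weeks as the upper end. Eight weeks otherwise appears only as the upper end of usual practice in the background. Section 8.1 refers the reader to 8.3 for the early stopping rules.

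**Step 3. How the two versions relate.** For a patient with lead-in chemotherapy the criteria are nested: a delay past day 56 is also past day 42. The versions therefore disagree in one direction only. The disagreement arises when at least 2 of the first 6 patients meet the 8.3 criteria but fewer than 2 meet the 5.1.4 criteria, because some delays fall on days 43-56.

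**Step 4. What the difference could do to the chance of stopping (illustration only).** The documents give no delay rates, so every rate here is an assumption. Take the delay criterion alone, six patients who all have lead-in chemotherapy, and independent patients with the same probability p:

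P(at least 2 of 6) = 1 − (1 − p)^6 − 6p(1 − p)^5

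At p = 0.20 this is 1 − 0.2621 − 0.3932 = 0.345. At p = 0.10 it is 1 − 0.5314 − 0.3543 = 0.114.

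| Assumed delay past 6 weeks | Assumed delay past 8 weeks | P(stop), 8.3 | P(stop), 5.1.4 |
|---|---|---|---|
| 20% | 5% | 0.345 | 0.033 |
| 20% | 10% | 0.345 | 0.114 |
| 30% | 15% | 0.580 | 0.224 |
| 40% | 20% | 0.767 | 0.345 |

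The size of the gap depends entirely on how many delays fall in the two-week band. If none do, the two versions give the same answer.

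**Step 5. Patients without direct lead-in chemotherapy.** Inclusion 2 requires earlier oxaliplatin-based chemotherapy of everyone; 2a does not require it to lead directly into the study.
- Section 5.1.4 has no if-applicable qualifier, so read literally its 56 days apply to every patient. If chemotherapy ended more than 56 days before C1D1, the window closed before the first study dose.
- Section 8.3 is qualified by if applicable and names no other clock. When the qualifier excludes a patient, the bullet can be read as dropping the delay criterion, or as counting any toxicity-related delay from the planned surgery date.
- Table 10 plans surgery 7-14 days after C1D1. Sections 5.1.3 and 6.1.4 say about 2 weeks, minimum 1 week. These are scheduling statements, and the stopping rule does not refer to them.

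**The case against.** The strongest reply is that the conflict has little practical force. Because the criteria are nested, following 8.3 satisfies both sections. Section 5.1.4 never says that the study must continue when its own limit is not reached, and 8.1 names 8.3 as the place for stopping rules. In the scenario of two patients delayed to weeks 7-8, section 3.2 would also suspend accrual, whatever the cause of the delay, and the first 6 cases are reviewed during the pause. Weekly Site Committee review, six-weekly DSMC meetings (7.8) and the general termination criteria (6.8) sit behind that. All of this stands and limits the consequence. It does not reconcile the two numbers, and suspending accrual is not stated to be the same as stopping the study.

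Three stronger readings are tempting and are not supported.

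- A reader might infer that patients without lead-in chemotherapy have no limit at all. Step 5 shows otherwise: 5.1.4 literally gives 56 days, which fits them badly, and 8.3 is ambiguous. Failure to have resection because of attributed adverse events may also still count under the opening sentence of 8.3.
- A reader might convert the two limits into exact days of tolerance after C1D1 from the Table 10 windows. Those results depend on reading the windows strictly. The schema, 5.1.3 and 6.1.4 give the interval to surgery only approximately, and C1D1 may fall as early as day 7 after chemotherapy. Only the 14-day difference is robust.
- A reader might infer a further conflict over attribution, since the opening sentence of 8.3 counts patients who "experience Grade IV-V surgical complications according to Clavien-Dindo classification attributed to pembrolizumab"-based treatment, while the complication bullets do not mention attribution. The notes in both sections address this. Section 5.1.4 concedes that "it may be difficult to attribute any such complications to preoperative administration of pembrolizumab-based treatment", and 8.3 adds that "the occurrence of such events may not necessarily require stopping the study early, but will be discussed amongst members of the JSC". Rewriting who must show attribution would change the sponsor's rule, so it is not part of this correction.

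**Conclusion.** The inconsistency is real and lies in current protocol text: one 2-of-6 stopping rule with limits of 56 and 42 days after final chemotherapy. Its certain size is 14 days. Its effect on the chance of stopping cannot be stated from the documents, and the probabilities above only illustrate it under assumed rates. It should be fixed because it is a decision threshold in a safety rule for patients treated with curative intent. The safeguards in 3.2, 5.1.4, 7.8 and 8.3 make it unlikely that such delays would go unexamined, so the documents do not support a claim that the trial would run on unchecked.

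That 6 weeks is the intended limit is an inference from the agreement of the other sections and the reference in 8.1. The background in 1.3 gives 8 weeks some support, so the sponsor should confirm. The clock for patients without lead-in chemotherapy is a secondary matter of ambiguity and poor fit.

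**What to change.** 1. In 5.1.4, change 8 weeks to 6 weeks, or replace the delay bullet with a reference to 8.3 as the governing rule. The cross-reference is safer because it leaves one copy of the threshold to maintain. The sponsor should confirm 6 weeks.

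2. In 8.3, state the clock for patients without direct lead-in chemotherapy. It should run from C1D1 and be tied to the surgery window already in Table 10 (7-14 days after C1D1). Any tolerance beyond day 14 is a clinical judgment for the sponsor; the protocol contains no number from which to derive it.

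Keep the 3.2 accrual suspension, the pause after the sixth patient, the exclusion of non-toxicity delays and the JSC discussion as they are.

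The cost is a few lines in 5.1.4 and 8.3, handled as an amendment with PRC and IRB approval under 9.4. It adds no patients, visits or procedures.
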